Appendix A: Tables

Table 1. Behavioral outcomes used for primary and secondary impact analyses research questions

Outcome name	Description of the outcome, including how it is operationalized	Source of the measure	Timing of measure
Current LARC use	
The protective outcome is operationalized as a dichotomous variable indicating whether a person reports currently using LARC (implant or IUD) or not currently using LARC.
 
The measure is calculated from the following item:
 
 • Which of the following methods of prescription birth control are you currently using? 
 ○ None: I am not currently using any of these methods ○ Oral contraceptives (for example, the pill) ○ The patch (for example, Ortho Evra) ○ The shot/injection (for example, Depo-Provera) ○ The ring (for example, NuvaRing) ○ The implant (for example, Implanon or Nexplanon) ○ IUD (for example, ParaGard, Skyla, or Mirena) 
A person who selects either The implant or IUD is given a value of 1 for the measure. A person who selects None, Oral contraceptives, The patch, The shot/injection, or The ring is given a value of 0 for the measure.
 
The resulting variable is dichotomous with values 0 or 1, where 0 indicates a person who does not currently use a LARC and 1 indicates a person who does currently use a LARC.
 
Note: The analytic sample will include all respondents who have three-month follow-up data.
	Participant Questionnaire	Three-month follow-up (three months after enrollment)
Times having sex without condom	
The risk outcome is operationalized as the number of times in the past three months a person reports having any type of sex without using a condom.
 
The measure is calculated from the following items:
 
 • In the past 3 months, how many times have you had vaginal sex without using a condom? 	Participant Questionnaire	Three-month follow-up (three months after enrollment)

- In the past 3 months, how many times have you had oral sex without using a condom?
- In the past 3 months, how many times have you had anal sex without using a condom?

The measure is calculated by summing the total number of times a person reported not using a condom during vaginal, oral and anal sex.

The resulting variable is continuous with values that range from 0 to k , where 0 indicates that a person has not engaged in sex without a condom in the past three months, and k indicates the number of times the person has engaged in sex without a condom (risk behavior) in the past three months.

Note: The analytic sample will include all respondents who have three-month follow-up data. Persons who indicate they have not had sex will be considered to have participated in the risk behavior 0 times (i.e., they did not engage in sex without a condom).

STI testing	
The protective outcome is operationalized as a dichotomous variable indicating whether a person reports having been tested for STIs in the past three months or not having been tested.
 
The measure is calculated from the following item:
 
 • Have you been tested for STIs/STDs other than HIV in the past 3 months? 
A person who selects either Yes is given a value of 1 for the measure. A person who selects No is given a value of 0 for the measure.
 
The resulting variable is dichotomous with values 0 or 1, where 0 indicates a person who has not been tested for STIs/STDs in the past three months and 1 indicates a person who has been tested for STIs/STDs.
 
Note: The analytic sample will include all respondents who have three-month follow-up data.
	Participant Questionnaire	Three-month follow-up (three months after enrollment)
Use of dual methods of protection	
The protective outcome is operationalized as the proportion of times in the past three months a person reports using both a condom and prescription birth control during vaginal sex out of total times reported having vaginal sex.
	Participant Questionnaire	Three-month follow-up (three months after enrollment)

The measure is calculated from the following two items:

- In the past three months, how many times have you had vaginal sex?
- Please think about how many times you said you had vaginal sex in question 20. Of the times you had vaginal sex, how many times would you say you used dual methods of protection – that is, how many times did you use both a condom and one of the listed methods of prescription birth control at the same time?

The resulting variable is a continuous proportion with values that range from 0 to 1, where 0 indicates that a person has used dual methods of protection 0% of the time during vaginal sex in the past three months, and 1 indicates the person has used dual methods of protection 100% of the time during vaginal sex in the past three months.

Note: The analytic sample will only include respondents who have three-month follow-up data and who indicate in their three-month follow-up questionnaire that they have had vaginal sex in the past three months. Persons who indicate they have never had vaginal sex or have not had vaginal sex in the past three months will be excluded from the construction of this measure.

Use of other effective contraceptive methods

The protective outcome is operationalized as a dichotomous variable indicating whether a person reports currently using prescription birth control methods beyond LARC or not currently using any prescription birth control methods.

*Participant
Questionnaire*

Three-month follow-up
(three months after enrollment)

The measure is calculated from the following item:

- Which of the following methods of prescription birth control are you currently using?
 - None: I am not currently using any of these methods
 - Oral contraceptives (for example, the pill)
 - The patch (for example, Ortho Evra)
 - The shot/injection (for example, Depo-Provera)
 - The ring (for example, NuvaRing)
 - The implant (for example, Implanon or Nexplanon)
 - IUD (for example, ParaGard, Skyla, or Mirena)

A person who selects either *Oral contraceptives*, *The patch*, *The shot/injection*, or *The ring* is given a value of 1 for the measure. A person who selects *None* is given a value of 0 for the measure.

The resulting variable is dichotomous with values 0 or 1, where 0 indicates a person who does not currently use any prescription birth control methods and 1 indicates a person who uses non-LARC prescription birth control methods.

Note: The analytic sample will only include respondents who have three-month follow-up data and who indicate in their three-month follow-up questionnaire that they are currently not using any birth control or using one of the non-LARC methods. Persons who indicate they use LARC methods will be excluded from the construction of this measure.

Table 2. Covariates included in primary and secondary impact analyses

Covariate	Description of the covariate and how it will be used as a covariate in the analysis	Rationale for inclusion
Behavioral outcomes at baseline		
Current LARC use	
The protective outcome is operationalized as a dichotomous variable indicating whether a person reports currently using LARC (implant or IUD) or not currently using LARC.
 
The measure is calculated from the following item:
 
 • Which of the following methods of prescription birth control are you currently using? 
 ○ None: I am not currently using any of these methods ○ Oral contraceptives (for example, the pill) ○ The patch (for example, Ortho Evra) ○ The shot/injection (for example, Depo-Provera) ○ The ring (for example, NuvaRing) ○ The implant (for example, Implanon or Nexplanon) ○ IUD (for example, ParaGard, Skyla, or Mirena) 
A person who selects either The implant or IUD is given a value of 1 for the measure. A person who selects None, Oral contraceptives, The patch, The shot/injection, or The ring is given a value of 0 for the measure.
 
The resulting variable is dichotomous with values 0 or 1, where 0 indicates a person who does not currently use a LARC and 1 indicates a person who does currently use a LARC.
	
Current LARC use is included in the primary impact analysis as the pre-intervention or baseline measure of the behavioral outcome; it is included in the models so that individual-level change or difference can be assessed at the three-month follow-up.

Times having sex without condoms	
The risk outcome is operationalized as the number of times in the past three months a person reports having any type of sex without using a condom.
 
The measure is calculated from the following items:
 
 • In the past 3 months, how many times have you had vaginal sex without using a condom? • In the past 3 months, how many times have you had oral sex without using a condom? 	
Times having sex without condoms is included in the primary impact analysis as the pre-intervention or baseline measure of the behavioral outcome; it is included in the models so that individual-level change or difference can be assessed at the three-month follow-up.

Covariate	Description of the covariate and how it will be used as a covariate in the analysis	Rationale for inclusion
	
 • In the past 3 months, how many times have you had anal sex without using a condom? 
The measure is calculated by summing the total number of times a person reported not using a condom during vaginal, oral and anal sex.
 
The resulting variable is continuous with values that range from 0 to k, where 0 indicates that a person has not engaged in sex without a condom in the past three months, and k indicates the number of times the person has engaged in sex without a condom (risk behavior) in the past three months.
	
STI testing	
The protective outcome is operationalized as a dichotomous variable indicating whether a person reports having been tested for STIs in the past three months or not having been tested.
 
The measure is calculated from the following item:
 
 • Have you been tested for STIs/STDs other than HIV in the past 3 months? 
A person who selects either Yes is given a value of 1 for the measure. A person who selects No is given a value of 0 for the measure.
 
The resulting variable is dichotomous with values 0 or 1, where 0 indicates a person who has not been tested for STIs/STDs in the past three months and 1 indicates a person who has been tested for STIs/STDs.
	
STI testing is included in the primary impact analysis as the pre-intervention or baseline measure of the behavioral outcome; it is included in the models so that individual-level change or difference can be assessed at the three-month follow-up.

Use of dual methods of protection	
The protective outcome is operationalized as the proportion of times in the past three months a person reports using both a condom and prescription birth control during vaginal sex out of total times reported having vaginal sex.
 
The measure is calculated from the following two items:
 
 • In the past three months, how many times have you had vaginal sex? • Please think about how many times you said you had vaginal sex in question 20. Of the times you had vaginal sex, how many 	
Use of dual methods of protection is included in the secondary impact analysis as the pre-intervention or baseline measure of the behavioral outcome; it is included in the models so that individual-level change or difference can be assessed at the three-month follow-up.

Covariate	Description of the covariate and how it will be used as a covariate in the analysis	Rationale for inclusion
	
times would you say you used dual methods of protection – that is, how many times did you use both a condom and one of the listed methods of prescription birth control at the same time?
 
The resulting variable is a continuous proportion with values that range from 0 to 1, where 0 indicates that a person has used dual methods of protection 0% of the time during vaginal sex in the past three months, and 1 indicates the person has used dual methods of protection 100% of the time during vaginal sex in the past three months.
	
Use of other effective contraceptive methods	
The protective outcome is operationalized as a dichotomous variable indicating whether a person reports currently using prescription birth control methods beyond LARC or not currently using any prescription birth control methods.
 
The measure is calculated from the following item:
 
 • Which of the following methods of prescription birth control are you currently using? 
 ○ None: I am not currently using any of these methods ○ Oral contraceptives (for example, the pill) ○ The patch (for example, Ortho Evra) ○ The shot/injection (for example, Depo-Provera) ○ The ring (for example, NuvaRing) ○ The implant (for example, Implanon or Nexplanon) ○ IUD (for example, ParaGard, Skyla, or Mirena) 
A person who selects either Oral contraceptives, The patch, The shot/injection, or The ring is given a value of 1 for the measure. A person who selects None is given a value of 0 for the measure.
 
The resulting variable is dichotomous with values 0 or 1, where 0 indicates a person who does not currently use any prescription birth control methods and 1 indicates a person who uses non-LARC prescription birth control methods.
	Use of other effective contraceptive methods is included in the secondary impact analysis as the pre-intervention or baseline measure of the behavioral outcome; it is included in the models so that individual-level change or difference can be assessed at the three-month follow-up.
Individual level covariates		

Covariate	Description of the covariate and how it will be used as a covariate in the analysis	Rationale for inclusion
Age	
The variable is measured as the respondent's age in years at screening.
 
The measure is constructed from the following item on the VHS Eligibility Screening Form:
 
 • What is your date of birth? 
The variable is calculated by subtracting the reported date of birth given from the date when the screening was completed.
 
The resulting variable is continuous with values ranging from 18 to 19.
	
Research has shown that likelihood of engaging in sex increases with age and use of condoms declines (Brewster 1999; Kirby 2007; Miller et al 1998; Scott-Jones and White 1990)

Black/African American	
The measure is operationalized as a dummy variable, where 0 = identify as another race/do not identify race; 1 = identify as Black/African American.
 
The measure is taken directly from the following item on the VHS Eligibility Screening Form:
 
 • What is your race and ethnicity? (Study coordinators can select more than one based on participant's response) 
 ○ White ○ Black or African American ○ Hispanic, Latino, or of Spanish origin ○ American Indian or Alaska Native ○ Asian ○ Native Hawaiian or Pacific Islander ○ Unknown ○ Some other race/ethnicity (specify) 
Variable will be coded as 1 if participant self-identified as Black or African American, regardless as to whether other races/ethnicities are specified; if Black or African American is not selected, the response will be coded as 0.
	
Research has shown that Black/African American and Hispanic adolescents are more likely to engage in sex during adolescence, initiate sexual activity at a younger age, and less likely to use contraception of any kind (Blum 2000; Brewster 1999; Hogan et al 2000; Kirby 2007; Scott Jones and White 1990)

Covariate	Description of the covariate and how it will be used as a covariate in the analysis	Rationale for inclusion
Hispanic, Latino or of Spanish origin	
The measure is operationalized as a dummy variable, where respondents who identify as Hispanic, Latino, or of Spanish origin are coded as 1 and coded as 0 otherwise.
 
The measure is taken directly from the following item on the VHS Eligibility Screening Form:
 
 • What is your race and ethnicity? (Study coordinators can select more than one option based on participant's response) 
 ○ White ○ Black or African American ○ Hispanic, Latino, or of Spanish origin ○ American Indian or Alaska Native ○ Asian ○ Native Hawaiian or Pacific Islander ○ Unknown ○ Some other race/ethnicity (specify) 
Variable will be coded as 1 if participant self-identified as Hispanic, Latino, or of Spanish origin, regardless as to whether other races/ethnicities are specified; if Hispanic, Latino, or of Spanish origin is not selected, the response will be coded as 0.
	
High school education	
This measure is operationalized as a dummy variable, where individuals with a high school education are coded as 1 and all others are coded as 0.
 
The measure is taken directly from the following item on the Baseline Participant Questionnaire:
 
 • What is the highest degree or level of school you have completed (if currently enrolled, select the previous grade completed or degree received)? 
 ○ Grade 9-12 (please specify grade) ○ GED or alternative credential ○ Some college credit, but less than 1 year of credit 	

Covariate	Description of the covariate and how it will be used as a covariate in the analysis	Rationale for inclusion
	
 ○ 1 or more years of college credit, no degree ○ Associate's degree ○ Bachelor's degree ○ Other (specify) 
Participants who select Grade 9-12 will be coded as 0=has not completed high school; all others will be coded as 1=has completed high school.
	
Blocking Covariates		
Region	
The measure is operationalized a set of $n-1$ dummy variables, where n refers to the number of VHS regions over the course of the evaluation period.
 
Data for the measure are obtained from the Enrollment Log Database.
 
Each dummy will be coded as 1 if the individual is enrolled in a particular region and 0 otherwise. Region 1 is the reference variable. Dummy variables will be grand mean centered so that the intercept will then reflect the un-weighted mean site effect.
	Randomization is blocked by region.

Table 3: Data Editing Rules

The following table provides PRG's general rules for editing data based upon responses given.

Category	Data editing rule
No response given to an item (coded as .f)	If data from a related variable can be used to infer a value, data will be logically edited. Otherwise, the value will be left as missing.
Invalid items (coded as .i)	Adjust missing baseline values
Outlying items (Outlier indicator variable coded as 1)	Keep in benchmark analysis; run sensitivity analyses excluding outliers
Inconsistent across-time items (coded as .k)	Adjust missing baseline values
Unreliable cases (Unreliable indicator variable codes as 1)	Exclude case from benchmark analysis; run sensitivity analyses including unreliable cases

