²⁷ We will code missing responses with a unique missing code that identifies or flags these missing values according to the reason they are missing (i.e., nonresponse, invalid, inconsistent). Unreliable data are not recoded to missing, rather cases deemed unreliable are coded as 1 in an indicator variable, treated as unit missing, and excluded from analysis. See the *Data cleaning* section or Table 3 in Appendix A for details on how missing data are coded.

²⁸ For item missing values, we will only report prevalence of missing and inconsistent data for variables that are included in our model specifications and could therefore influence the constitution of the analytic sample.

variable coding below; details on variable construction can be found in Table 2 in Appendix A.

Demographic:

- Age at screening (continuous; range 18-19)²⁹
- Identify as Black/African American at screening (0 = identify as another race/do not identify race; 1 = identify as Black/African American)³⁰
- Identify as Hispanic, Latino, or of Spanish origin at screening (0=do not identify as Hispanic, Latino, or of Spanish origin; 1= identify as Hispanic, Latino, or of Spanish origin)³¹
- Completed high school (0 = has not completed high school; 1= has completed high school)

Sexual Behavior:

- Ever had sex (0=never had vaginal, anal, or oral sex; 1=has had vaginal, anal, and/or oral sex in lifetime);

Baseline Outcome Measures

In addition to the demographic and sexual behavior measures, we will assess baseline equivalency of the baseline observations of the outcome measures. We provide details on variable coding below; details on variable construction can be found in Table 2 in Appendix A.

- *Times having sex without condom in the past 3 months* at baseline (continuous; values range 0 to k , where 0= has had sex without condoms 0 times in past 3 months and k = number of times having sex without condoms in past 3 months)
- *Current LARC use* at baseline (0= not currently using a LARC; 1= currently using a LARC)
- *STI Testing in the past 3 months* at baseline (0=not tested for STIs/STDs in past 3 months; 1= tested for STIs/STDs in past 3 months)

Balance Assessment Methods

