Y_{Pre} – The baseline measure of the outcome variable of interest reported by participant i at baseline (see Table 2 for full details on the variable construction); variable will be re-centered at the grand mean for analysis.

T – A dummy treatment indicator variable whose value equals 1 if the participant is randomized into the treatment group and zero otherwise.

X – A p vector of baseline (i.e., measured prior to receiving intervention or exogenous to treatment) participant-level covariates as well as blocking variables to account for the variation in outcomes associated with these groups. These covariates, listed in detail in Table 2 in Appendix A, will include:

- a) Age – self-reported age (based on date of birth) at screening (continuous; range 18-19); variable will be re-centered at the grand mean for analysis.
- b) Race – self-reported as Black/African American at screening (0 = identify as another race/do not identify race; 1 = identify as Black/African American); each of the variables will be re-centered at the grand mean for analysis.
- c) Ethnicity – self-reported as Hispanic, Latino, or of Spanish origin at screening (0=do not identify as Hispanic/Latino/Spanish origin; 1=identify as Hispanic, Latino, of Spanish origin); variable will be re-centered at the grand mean for analysis.
- d) High school education – self-reported education at baseline. A dummy variable (0= has not completed high school; 1= has completed high school); variable will be re-centered at the grand mean for analysis.
- e) Region – An $n-1$ vector of region indicator dummy variables that are coded one if the intervention was delivered at region n and coded zero otherwise. Region 1 is the reference category and is excluded from analysis. The dummy variables will be mean-centered for analysis to facilitate interpretation.⁴¹

β_0 – The intercept term, which represents, depending on the outcome measure of interest in the analysis, the outcome for the average control participant with all other variables in the model held constant at their mean.

β_1 – This is the parameter estimate of substantive interest. β_1 represents, depending on the outcome measure of interest in the analysis, either: 1) the adjusted mean difference in

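### The high-school covariate codes women who report completing grade 12 as non-completers, and codes any 'Other' answer as completion, against the variable's own definition (minor)

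*SAP*

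**What the plan says.** In SAP Appendix A, Table 2, the row for high school education takes the covariate from one baseline questionnaire item: "What is the highest degree or level of school you have completed (if currently enrolled, select the previous grade completed or degree received". The first response option is "Grade 9-12 (please specify grade", with the grade written in. The next is "GED or alternative credential". Two levels of college credit, two degrees and "Other (specify" follow. No high school diploma option is printed.

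Under the coding rule, anyone choosing the grade option is coded 0, not completed, and "all others will be coded as 1=has completed high school".

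The same row defines the variable as 1 for women with a high school education. Section 4d lists it among the baseline-equivalence measures, labelled "0 = has not completed high school; 1= has completed high school". Section 4f(i) enters it as covariate d, "High school education – self-reported education at baseline", in the model for the three primary outcomes. Section 4g carries that model over to the secondary outcomes.

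**The concern.** The item asks what has been completed, and tells women still enrolled to give the previous grade completed. Taken at its word, an answer of grade 12 means that grade 12 is finished. The rule nonetheless gives it the same code as grades 9, 10 and 11, so it contradicts the label the SAP attaches to the variable. 'Other' fails in the opposite direction: it is coded as completion whatever is written, although the list has no option below grade 9.

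The women affected are not a fringe group by design. Section 3a restricts enrolment to ages 18 and 19, when grade 12 may well be the highest level completed.

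Two things are at stake. First, a sample characteristic would be reported under the wrong name: the adjusted means, p-value and Cox index promised in Section 4d would be presented as describing high school completion. Second, a covariate that is mismeasured relative to its label enters every primary and secondary model, where its purpose (footnote 39) is to sharpen the estimate.

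**Working it through.** **Step 1: apply the rule to each answer and compare it with the label.** The SAP states no figure that depends on this coding, so there is none to reproduce.

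| Answer | Code under Table 2 | Meaning of the label | Agree? |
|---|---|---|---|
| Grade 9, 10 or 11 | 0 | not completed | yes |
| Grade 12 | 0 | completed | no |
| GED or alternative credential | 1 | completed | yes |
| Any college credit, or a degree | 1 | completed | yes |
| Other, e.g. schooling below grade 9 | 1 | not completed | no |
| Other, e.g. a certificate taken after a diploma | 1 | completed | yes |

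**Step 2: look for a repair elsewhere.** Sections 4d and 4f(i) repeat the label but give no rule. Table 3 (data editing rules) covers missing, invalid, outlying, inconsistent and unreliable data. None of these separates grade 12 from grades 9-11 or says how 'Other' text is read. The sensitivity analysis without covariates (Section 4f(iv), item 1) removes the covariates as a set and does not test how this one is coded.

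**Step 3: scale of the misreported percentage.** The inputs are assumptions, because the SAP gives no education distribution. Let t be the true completion share and g the share of the sample whose highest level is grade 12. Suppose all of the latter choose the grade option and no 'Other' answer is miscoded. Then:

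- coded share c = t − g
- completers coded 0 = g / t
- correlation of coded with true completion = √[(c/(1−c)) × ((1−t)/t)]

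With t = 0.85:

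| g | c | g / t | correlation |
|---|---|---|---|
| 0.30 | 0.55 | 0.30/0.85 = 35% | 0.46 |
| 0.40 | 0.45 | 0.40/0.85 = 47% | 0.38 |
| 0.50 | 0.35 | 0.50/0.85 = 59% | 0.31 |

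Over a wider grid (true completion 70-90%, and 20-60% of completers having grade 12 as their highest level), 32-84% of the women coded as non-completers would in fact be completers.

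**Step 4: effect on precision.** Suppose true completion explains a share R² of outcome variance and the coded version keeps a fraction k of that. The treatment-effect standard error then rises by the factor √[(1 − kR²)/(1 − R²)].

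- Mildest case, R² = 0.01 and k = 0.60: √(0.994/0.99) = 1.002, a rise of 0.2%.
- Worst case, R² = 0.05 and k = 0.05: √(0.9975/0.95) = 1.025, a rise of 2.5%.

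On the Step 3 grid k runs from about 0.06 to 0.55, inside the range used here. R² is also assumed.

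**The case against.** The strongest reply is that little follows from the miscoding, and much of it stands.

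- **Other routes to code 1.** A reader might infer that a diploma holder without college has no choice but the grade option, so that the percentage is low by exactly the grade-12 share. The documents do not support that. She could choose the alternative-credential option or write her diploma under 'Other', and either is coded 1. Wrongly coded 'Other' answers also push the percentage up. For many 'Other' answers, code 1 may be right.
- **What the variable measures.** One might conclude that it mostly captures GED or college attendance. That depends on shares the SAP does not give.
- **Balance between arms.** One might conclude that the equivalence check is invalid. It is not: the variable is measured before treatment and coded identically in both arms, so the contrast is a fair comparison of the variable as coded. What is wrong is the label and the percentage shown under it.
- **Precision.** What counts is prediction of the outcomes, not agreement with true completion. Table 2 prints no rationale for this covariate, and nothing shows that true completion predicts the outcomes better than the coded split does. It is also one of several covariates, alongside the baseline outcome, age, race, ethnicity and region.

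The reply does not remove the contradiction itself. Nothing in the SAP directs diploma holders away from the grade option, and whoever reports grade 12 is coded against the label. Even if the questionnaire carried a diploma option that Table 2 does not list, grade 12 would still be coded 0 and 'Other' 1.

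**Conclusion.** The point holds as a minor one: the coding rule contradicts the SAP's own definition for grade 12, and for 'Other' answers that describe less than completion. As written, the completed-high-school percentage and its equivalence row would not describe high school completion. The percentage would be understated to the extent that women whose highest level is grade 12 select the grade option. The amount cannot be derived from the SAP; 35-55% shown against 85% true completion is an illustration resting on the assumptions in Step 3 of the working.

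A reader might infer bias in the estimated effect of *Plan A*. The document gives no ground for that: this is a baseline covariate in a randomized comparison, coded the same way in both arms. The loss of precision is uncertain and likely small, about 0.2-2.5% in the standard error under the assumed R² of 1-5%. Sample size, significance level and decision rules are unaffected.

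**What to change.** Rewrite the coding rule in Table 2:

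- **Code 1:** written-in grade is 12; GED or alternative credential; any college credit; any degree.
- **Code 0:** written-in grade is 9, 10 or 11.
- **'Other':** classify from the text, by someone masked to arm.
- **Missing:** a grade option with no grade given, or 'Other' text that is blank or cannot be classified. These go to the dummy-variable adjustment already planned in Section 4c(v), step 5.

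The cost is a wording change and one recode, because the grade is already collected. The remaining weakness is that some women still in grade 12 may overlook the instruction and write their current grade, so a little misclassification would persist. The report should say so beside the row.
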